### 6.2.5 Relapse

- Relapse is defined as:

- $\Delta$  ASDAS  $\geq 0,6$  (compared to ASDAS at time of sustained clinical remission) and ASDAS  $\geq 1,3$  (17)

AND

- PASS (= patient acceptable symptom state) for the upcoming 6 months is NO (meaning: would the patient be satisfied if current clinical situation would continue for the next 6 months)

AND

- Expert opinion: the assessing physician believes that  $\Delta$  ASDAS reported by the patient is most probably related to a relapse of spondyloarthritis. If not, an alternative hypothesis/probable diagnosis must be provided.

- In case of relapse, the time point will be registered in the study, extra blood samples will be drawn (2x5mL serum; site specific: 3x10mL heparin blood only in Ghent University Hospital) and the

subjects will be treated according to the routine clinical practice. In reality, this will most likely match the last remission-inducing treatment of the subject.

### **6.2.6 No remission achieved**

When the subject is still not in sustained remission after 48 weeks of golimumab treatment, defined as ASDAS < 1.3 on 2 consecutive study visits, the patient will stop participating in this study and will be followed in the routine clinical practice.

### **6.2.7 Procedures**

#### **6.2.7.1 Screening visit**

- ICF
- Check fulfillment of the inclusion and exclusion criteria
- Anamnesis
- Medical and family history
- Demographic data
- Symptom duration
- Current and past medication (NSAID): dosage and duration
- Clinical examination:
  - o weight, length, vital symptoms (blood pressure, heart frequency)
  - o BASMI
  - o Total tender and swollen joint count (TJC/SJC) (78)
  - o Dactylitis assessment
  - o MASES + plantar fascia + quadriceps and patellar tendon
- Assessment of work participation (site-specific: only in Ghent University Hospital).
- Questionnaires: Bath Ankylosing Spondylitis Disease Activity Index (BASDAI), Bath Ankylosing Spondylitis Functional Index (BASFI), Patient global assessment of disease activity, patient global pain assessment. Site-specific (only in Ghent University Hospital): Work Productivity and Activity Impairment (WPAI), health care consumption, EQ5D.
- Laboratory investigation (incl. 4x5mL serum + 3x4mL EDTA for additional research)
- Imaging: MRI SI joints (if not already done), chest X-ray
- Mantoux tuberculin test
- Pregnancy test for female subjects (on blood sample)

#### **6.2.7.2 Baseline**

[figure not shown]
- Laboratory investigation (site-specific: only in Ghent University Hospital 4x10mL heparin blood for additional research)
- Stool sample
- Ileocolonoscopy including for all sites routine biopsies for pathological examination (4 biopsies in ileum, 8 biopsies in colon) and extra biopsies for RNA sequencing (2 biopsies in ileum, 2 biopsies in colon) will be taken. Additional for functional analyses, site specific (only in Ghent University Hospital), also 6 biopsies in ileum and 6 biopsies in colon will be taken.
- Start treat-to-target approach

[figure not shown]
- AND if baseline visit is performed more than 4 weeks after the screening visit:
  - o Anamnesis
  - o Current and past medication (NSAID): dosage and duration
  - o Clinical examination:
    - weight, length, vital symptoms (blood pressure, heart frequency)
    - BASMI
    - Total tender and swollen joint count (TJC/SJC) (78)
    - Dactylitis assessment
    - MASES + plantar fascia + quadriceps and patellar tendon
  - o Questionnaires: cfr. 6.2.7.1 (excl. WPAI, health care consumption and EQ5D)

#### **6.2.7.3 Follow-up visits**

- Anamnesis
- Current and past medication: dosage and duration
- Clinical examination:
  - o weight, length, vital symptoms (blood pressure, heart frequency)
  - o BASMI
  - o Total tender and swollen joint count (TJC/SJC) (78)
  - o Dactylitis assessment
  - o MASES + plantar fascia + quadriceps and patellar tendon
- Questionnaires: cfr. 6.2.7.1 (WPAI, health care consumption and EQ5D are site-specific (only in Ghent University Hospital) and only at time of switch from NSAID to anti-TNF and at time of sustained remission).
- Assessment of work participation (site-specific: only in Ghent University Hospital) only at time of switch from NSAID to anti-TNF and at time of sustained remission.
- Laboratory investigation (incl. 2x5mL serum at every follow-up visit for additional research; site-specific: only at Ghent University Hospital 3x10mL heparin after 4 weeks of NSAIDs, 6 months of golimumab, at time of sustained clinical remission (if and on the same day as the second ileocolonoscopy incl. biopsies cfr. 6.2.7.2) and at time of relapse))
- Stool sample (after 4 weeks NSAID, 6 months golimumab and at time of relapse)

### 6.3 Flowchart

## 6.4 Study table

	Clinical examination (incl. BASMI)	Patient questionnaires	Blood: 4x5mL serum + 3x4mL EDTA	Blood: 2x5mL serum	Blood: 4x10mL heparin †	Pregnancy test (for female subjects)	Screening tuberculosis: chest X-ray and Mantoux	Stool sample	Ileocolonoscopy o	ASDAS	MRI SIG	Medication (golimumab) (starts after treatment failure on NSAIDs)
Screening	X	X	X			X	X			X	X *	
Baseline	X	X			X			X	X	X		
Follow-up visits	X	X		X						X		X (every 4 weeks)
Extra after 4 weeks NSAIDs					X (only 3 tubes)			X				
Extra after 6 months anti-TNF					X (only 3 tubes)			X				
Extra at remission					X (only 3 tubes, if and on same day as colonoscopy)				If first ileocolonoscopy was positive		X	
Extra at relapse	X	X		X	X (only 3 tubes)			X		X		

† Site-specific: only in Ghent University Hospital (Center 01); \* MRI SIG at screening if not already done in the context of diagnosis; o Ileocolonoscopy including for all sites biopsies for pathological examination (4 in ileum, 8 in colon) and RNA sequencing (2 in ileum, 2 in colon). Additional for functional analyses (site specific: only in Ghent University Hospital: 6 in ileum, 6 in colon).

## 6.5 Medication

- NSAID therapy will be given orally in full anti-inflammatory dose according to the routine clinical practice.
- Golimumab, provided by MSD, will be given subcutaneous at the dose of 50 mg every 4 weeks.

### 6.5.1 Composition and dosing

Golimumab is a human monoclonal antibody (mab) with an IgG1 heavy chain isotype and a kappa light chain isotype that binds TNF $\alpha$  with high affinity and specificity. The molecule is produced by a stable, recombinant murine cell line transfected with DNA coding for the heavy and light chains of the mab. Golimumab is supplied as a liquid in a prefilled syringe (PFS) for subcutaneous administration. Each prefilled syringe contains 50mg (0.5mL fill of liquid) golimumab, histidine, sorbitol and polysorbate 80 at pH 5.5. No preservatives are present. The prefilled syringe with golimumab will be administrated subcutaneously every 4 weeks. This is the same dose/regimen used as in the previously performed Phase III golimumab studies.

### 6.5.2 Producer

Golimumab (Simponi): Janssen Biologics B.V.

### 6.5.3 Distributor

Golimumab: Janssen Biologics B.V.

### 6.5.4 Packaging

Golimumab will be supplied as a sterile liquid in a 0.5mL single-use prefilled syringe for subcutaneous administration.

### 6.5.5 Administration way

Golimumab will be administrated subcutaneously every 4 weeks.

### 6.5.6 Labelling

The following particulars will be added to the original packaging, but will not obscure the original labelling:

- I) Studie/Etude Go-Gut EUDRACT nr: 2017-001728-23
- II) Naam/nom SPONSOR: Prof. dr. [name] – UGent
- III) Naam/nom Dr.:
- IV) Centrum/centre:
- V) Patient Nr./N° patient:
- VI) Bezoek Nr./N° de visite:

Alleen voor klinisch onderzoek/Uniquement recherche biomédicale

### 6.5.7 Storage conditions

Golimumab will be stored in a locked refrigerator, which will be temperature-controlled by using a continuous temperature logger (2 °C to 8 °C) in original carton until time of use. It will be protected from light. It will be not frozen or shaken.

### 6.5.8 Known side effects of the medication

For the known side effects of golimumab we refer to those described in the latest update of the SmPC available on the EMA website.

Upper respiratory tract infection was the most common adverse drug reaction (ADR) reported in the controlled Phase III rheumatoid arthritis (RA), psoriatic arthritis (PsA), and AS studies through week 16, occurring in 7.2% of golimumab treated patients as compared with 5.8% of control patients. The most serious ADRs that have been reported for Simponi include serious infections (including sepsis, pneumonia, TB, invasive fungal and opportunistic infections), demyelinating disorders, lymphoma, HBV reactivation, CHF, autoimmune processes (lupus-like syndrome) and hematologic reactions. ADRs observed in clinical studies and reported from world-wide post-marketing use of golimumab are listed in Table 1. Within the designated system organ classes, the adverse drug reactions are listed under headings of frequency and using the following convention: Very common ( $\geq 1/10$ ); Common ( $\geq 1/100$  to  $< 1/10$ ); Uncommon ( $\geq 1/1,000$  to  $< 1/100$ ); Rare ( $\geq 1/10,000$  to  $< 1/1,000$ ); Very rare ( $< 1/10,000$ ); Not known (cannot be estimated from the available data).

**Table 1**

**Tabulated list of ADRs**

**Infections and infestations**

*Very common:* Upper respiratory tract infection (nasopharyngitis, pharyngitis, laryngitis and rhinitis)

*Common:* Bacterial infections (such as cellulitis), viral infections (such as influenza and herpes), bronchitis, sinusitis, superficial fungal infections

*Uncommon:* Septic shock, sepsis, tuberculosis, lower respiratory tract infection (such as pneumonia), opportunistic infections (such as invasive fungal infections [histoplasmosis, coccidioidomycosis, pneumocytosis], bacterial, atypical mycobacterial infection and protozoal), pyelonephritis, abscess, bacterial arthritis, infective bursitis

*Rare:* Hepatitis B reactivation

**Neoplasms, benign, malignant and unspecified**

*Uncommon:* Neoplasms (such as skin cancer, squamous cell carcinoma and melanocytic naevus)

*Rare:* Lymphoma, leukaemia, melanoma

*Not known:* Merckel cell carcinoma \*

**Blood and lymphatic system disorders**

*Common:* Anaemia

*Uncommon:* Leucopaenia, thrombocytopenia

*Rare:* Pancytopaenia

*Not known:* Aplastic anaemia \*

### **Immune system disorders**

*Common:* Allergic reactions (bronchospasm, hypersensitivity, urticaria), autoantibody positive

*Rare:* Serious systemic hypersensitivity reactions (including anaphylactic reaction), vasculitis (systemic), sarcoidosis

### **Endocrine disorders**

*Uncommon:* Thyroid disorder (such as hypothyroidism, hyperthyroidism and goitre)

### **Metabolism and nutrition disorders**

*Uncommon:* Blood glucose increased, lipids increased

### **Psychiatric disorders**

*Common:* Depression, insomnia

### **Nervous system disorders**

*Common:* Dizziness, paraesthesia, headache

*Uncommon:* Demyelinating disorders (central and peripheral), balance disorders, dysguesia

### **Eye disorders**

*Uncommon:* Visual disorders (such as blurred vision and decreased visual acuity), conjunctivitis, eye allergy (such as pruritis and irritation)

### **Cardiac disorders**

*Uncommon:* Congestive heart failure (new onset or worsening), arrhythmia, ischemic coronary artery disorders

### **Vascular disorders**

*Common:* Hypertension

*Uncommon:* Thrombosis (such as deep venous and aortic), Raynaud's phenomenon, flushing

**Respiratory, thoracic and mediastinal disorders**

*Uncommon:* Asthma and related symptoms (such as wheezing and bronchial hyperactivity)

*Rare:* Interstitial lung disease

---

**Gastrointestinal disorders**

*Common:* Constipation, dyspepsia, gastrointestinal and abdominal pain, nausea

*Uncommon:* Gastrointestinal inflammatory disorders (such as gastritis and colitis), gastro-oesophageal reflux disease, stomatitis

---

**Hepatobiliary disorders**

*Common:* Alanine aminotransferase increased, aspartate aminotransferase increased

*Uncommon:* Cholelithiasis, hepatic disorders

---

**Skin and subcutaneous tissue disorders**

*Common:* Alopecia, dermatitis, pruritus, rash

*Uncommon:* Psoriasis (new onset or worsening of pre-existing psoriasis, palmar/plantar and pustular), urticaria, vasculitis (cutaneous)

*Rare:* skin exfoliation

---

**Musculoskeletal and connective tissue disorders**

*Rare:* Lupus-like syndrome

---

**Renal and urinary disorders**

*Uncommon:* Bladder disorders

*Rare:* Renal disorders

---

**Reproductive system and breast disorders**

*Uncommon:* Breast disorders, menstrual disorders

---

**General disorders and administration site conditions**

*Common:* Pyrexia, asthenia, injection site reaction (such as injection site erythema, urticaria, induration, pain, bruising, pruritus, irritation and paraesthesia), impaired healing, chest discomfort

### **Injury, poisoning and procedural complications**

*Uncommon:* Bone fractures

\*: Observed with other TNF-blocking agents, but not observed in clinical studies with golimumab.

### **6.5.9 Fertility, pregnancy and lactation**

Data on fertility, pregnancy and lactation is described in the latest update of the SmPC available on the EMA website.

#### *Pregnancy*

There are no adequate data on the use of golimumab in pregnant women. Due to its inhibition of TNF, golimumab administered during pregnancy could affect normal immune responses in the newborn. Studies in animals do not indicate direct or indirect harmful effects with respect to pregnancy, embryonal/foetal development, parturition or postnatal development (see section 5.3 of SmPC).

Golimumab crosses the placenta. The use of golimumab in pregnant women is not recommended; golimumab should be given to a pregnant woman only if clearly needed. Following treatment with a TNF-blocking monoclonal antibody during pregnancy, the antibody has been detected for up to 6 months in the serum of the infant born by the treated woman. Consequently, these infants may be at increased risk of infection. Administration of live vaccines to infants exposed to golimumab in utero is not recommended for 6 months following the mother's last golimumab injection during pregnancy (see sections 4.4 and 4.5 of SmPC).

#### *Breastfeeding*

It is not known whether golimumab is excreted in human milk or absorbed systemically after ingestion. Golimumab was shown to pass over to breast milk in monkeys, and because human immunoglobulins are excreted in milk, women must not breast feed during and for at least 6 months after golimumab treatment.

#### *Fertility*

No animal fertility studies have been conducted with golimumab. A fertility study in mice, using an analogous antibody that selectively inhibits the functional activity of mouse TNF $\alpha$ , showed no relevant effects on fertility (see section 5.3 of SmPC).

Female participants are obliged to use contraception (oral, condom, IUD, ...) during the trial and until 6 months after the end of the trial. It's recommended to use double contraception by both the study participants and his/her partner.

Male participants: no risks concerning their partners' pregnancy.

### **6.5.10 Drug accountability**

The arrival of the study medication at the hospital pharmacy and the delivery to the study site (Department of Rheumatology) will be documented.

Drug accountability will be documented with the description of the batch number, date of administration to the patient, expiration date, the amount that is administered and the route of administration on a separate drug accountability log in order to maintain transparency.

## 6.6 Additional research

We will also examine non-invasive surrogate markers for gut inflammation and therefore we will collect blood samples at every study visit and stool samples at baseline, after 4 weeks of NSAID treatment, after 6 months of golimumab treatment and at time of relapse. These are to investigate e.g. the serum and fecal calprotectin levels and to perform in depth immunophenotyping (flow cytometry) and microbiome analysis. At the screening visit we will also collect additional blood samples for genetic analyses (relevant single nucleotide polymorphisms for overlap SpA and IBD). All analyses will be performed within a context relevant to the SpA concept.

All biological samples (blood, stool, gut biopsies and its derivatives) will be collected and stored pseudonymized during 20 years in the prospective research biobank of the department of rheumatology of the Ghent University Hospital (“Biobank van menselijk lichaamsmateriaal van patiënten met reumatische en/of musculoskeletale aandoeningen en gezonde controles”, EC 2019/0314, medical administrator: prof. dr. [name]). For the Imelda Hospital in Bonheiden (Center 03) these biological samples will first be stored on site as part of the prospective research biobank of the department of rheumatology of the Ghent University Hospital and shipped regularly (cooled transport at -80°C) in batch to the Gent University Hospital. The only exception concerns the gut biopsies from patients recruited at the Reuma Institute Hasselt (Center 02): these samples will be collected in Jessa Hospital, will be locally registered and stored (temporarily) in the Jessa Biobank (medical administrator: dr. [name] – no processing required except for immediate freezing) and will be transferred at once (cooled transport at -80°C) to the prospective research biobank of the department of Rheumatology of Ghent University Hospital after the study has ended. All analysis on additional study samples will be performed by the laboratory attached to the department of Rheumatology of the Ghent University Hospital (Medical Research Building, MRB). Some analyses will be conducted by the Flemish institute for biotechnology (VIB – Vlaams Instituut voor Biotechnologie).

## 7. Randomisation/blinding

- Randomisation: not applicable.
- Blinding: the investigator and his team as well as the patient will be blinded for the results of the ileocolonoscopy until the patient is switched to golimumab. Only in case of major abnormalities necessitating medical intervention, the investigator will be made aware of the results of the ileocolonoscopy earlier.

## 8. Prior and concomitant medication

The subject will be excluded if he/she had/used:

- Full anti-inflammatory dose of NSAIDs for more than 4 weeks for the duration of the axSpA symptoms.

- Prior exposure to any biologic therapy with a potential therapeutic impact on SpA, including anti-TNF therapy.
- Exposure to disease-modifying drugs (DMARDSS; i.e. methotrexate and sulfasalazine) in the last 3 months before the ileocolonoscopy.
- Exposure to systemic corticosteroid treatment in the last 14 days before the ileocolonoscopy.
- Infection(s) requiring treatment with intravenous antibiotics/antivirals/antifungals within 30 days prior to the baseline visit or oral antibiotics/antivirals/antifungals within 14 days prior to the baseline visit.

During the trial there are no specific limitations for concomitant therapy, with exception of the use of DMARDs or other biologicals, while on therapy with golimumab.

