### 3. Objectives and hypothesis

#### 3.1 Primary objectives

1. To describe and confirm the relationship between subclinical gut inflammation and axSpA.
2. To evaluate whether there is a higher need of anti-tumor necrosis factor  $\alpha$  (anti-TNF $\alpha$ ) treatment in axSpA patients with (subclinical) gut inflammation compared to those without.

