#### 3.4 Primary endpoint and timepoint of the endpoint.

Clinical remission, evaluated on 2 consecutive follow-up visits (interval: 12 weeks).

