### 6.1.3 Exclusion criteria

- Full anti-inflammatory dose of NSAIDs for more than 4 weeks for the duration of the axSpA symptoms.
- Prior exposure to any biologic therapy with a potential therapeutic impact on SpA, including anti-TNF therapy.
- Exposure to disease-modifying drugs (DMARDSS; i.e. methotrexate and sulfasalazine) in the last 3 months before the ileocolonoscopy.
- Exposure to systemic corticosteroid treatment in the last 14 days before the ileocolonoscopy.
- Infection(s) requiring treatment with intravenous antibiotics/antivirals/antifungals within 30 days prior to the baseline visit or oral antibiotics/antivirals/antifungals within 14 days prior to the baseline visit.
- Have a known hypersensitivity to human immunoglobulin proteins or other components of golimumab.
- History of central nervous system (CNS) demyelinating disease or neurologic symptoms suggestive of CNS demyelinating disease.
- History of listeriosis, histoplasmosis, chronic or active hepatitis B infection, hepatitis C infection, human immunodeficiency virus (HIV) infection, immunodeficiency syndrome, chronic recurring infections or active tuberculosis.
- Have a history of, or concurrent, chronic heart failure, including medically controlled, asymptomatic congestive heart failure.
- Evidence of dysplasia or history of malignancy (including lymphoma and leukemia) other than a successfully treated non-metastatic cutaneous squamous cell or basal cell carcinoma or localized carcinoma in situ of the cervix.
- Have received, or are expected to receive, any live virus or bacterial vaccination within 3 months prior to the first administration of study agent, during the trial, or within 6 months after the last administration of study agent.
- Positive pregnancy test at screening
- Female subjects who are breast-feeding or considering becoming pregnant during the study.
- Female subjects who do not use contraceptives.
- History of clinically significant drug or alcohol abuse in the last 12 months.
- Clinically significant abnormal screening laboratory results as evaluated by the investigator.
- Positive rheumatoid factor (RF) or anti-cyclic citrullinated peptide (anti-CCP) antibody at screening if the titers are crossing 3 times the upper limit of the normal.
- Subject with diagnosis and current symptoms of fibromyalgia.
- Any medical or psychological condition that, in the opinion of the investigator, could jeopardize or compromise the subject's ability to participate in this study.

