### 6.1.5 Limitations for the participants

There are no specific limitations for the participants other than the ones listed at section 6.1.3 Exclusion criteria, with the exception that there is an obligation for female subjects to use contraceptives.

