During the ileocolonoscopy, for all sites routine biopsies for pathological examination (4 biopsies in ileum, 8 biopsies in colon) and extra biopsies for RNA sequencing (2 biopsies in ileum, 2 biopsies in colon) will be taken. Additional for functional analyses, site specific (only in Ghent University Hospital), also 6 biopsies in ileum and 6 biopsies in colon will be taken. The investigators and the patient will be blinded for the results of this ileocolonoscopy until the subject is switched to golimumab. Only in case of major abnormalities necessitating medical intervention, the investigator will be made aware of the results of the ileocolonoscopy earlier. The central reader will make sure that 50% of the included patients will have subclinical gut inflammation and 50% of the patients will not have any subclinical gut inflammation. Additional blood samples will be drawn for functional analyses (site specific: only sampling of 4x10mL heparin blood in Ghent University Hospital) and 1 stool sample will be collected and stored pseudonymized in the prospective research biobank. After the trial has ended, all stool samples will be subject to biochemical and microbiome analyses (in one batch), performed by the laboratory attached to the department of Rheumatology of Ghent University Hospital.

At baseline, a treat-to-target principle will be installed. All subjects will receive a full anti-inflammatory dose NSAID for 2 weeks according to the routine clinical practice.

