Visits are scheduled on week 0, 2, 4, 16, 28, 40 and 52 ( $\pm$  2 weeks). If subjects have a clinically important improvement, defined as an ASDAS score < 1.3 or a decrease of at least 1.1 in ASDAS score resulting in a maximum of 2.1, subjects will continue with the same treatment. If subjects do not meet this disease activity state after a treatment with the first NSAID, a different NSAID will be installed at full anti-inflammatory dose during 2 weeks. Again, if subjects have a clinically important improvement (compared to the baseline situation before initiating the first NSAID therapy) after 2 weeks treatment with the second NSAID, subjects continue with this treatment. If this disease activity state is not reached at week 4, the NSAID treatment will be stopped and subjects will start treatment with golimumab (anti-TNF $\alpha$  therapy, 50mg every 4 weeks, subcutaneous injection) in monotherapy. At every trial visit routine blood tests (inflammatory markers at week 0, 2, 4 and a complete blood count, electrolytes, liver function, kidney function, inflammatory markers at screening, week 16, 28, 40 and 52) will be performed. Additional study samples for inflammatory markers (2x5mL serum) will be taken at every trial visit (except for the baseline visit at week 0, no additional serum samples) and stored in the prospective research biobank. After 4 weeks NSAID treatment, after 6 months golimumab treatment and at time of relapse stool samples (1 sample at each time point) and additional blood samples (site specific: only sampling of 3x10mL heparin blood in Ghent University Hospital) will be collected. The additional heparin blood samples are used immediately for functional analysis; the stool samples are stored pseudonymized in the prospective research biobank. After the trial has ended, all stool samples will be subject to biochemical and microbiome analyses (in one batch), performed by the laboratory attached to the department of Rheumatology of Ghent University Hospital.

Maximal study duration for a subject is 12 months.

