### 6.2.4 Remission

If subjects are in remission (ASDAS < 1.3) during the follow-up period on 2 consecutive study visits (with an interval of 12 weeks), subjects are considered to be in sustained clinical remission and golimumab or NSAID therapy will be stopped and a second ileocolonoscopy will be performed in those patients from whom the first colonoscopy showed (subclinical) gut inflammation. During the ileocolonoscopy, for all sites routine biopsies for pathological examination (4 biopsies in ileum, 8 biopsies in colon) and extra biopsies for RNA sequencing (2 biopsies in ileum, 2 biopsies in colon) will be taken. Additional for functional analyses, site specific (only in Ghent University Hospital), also 6 biopsies in ileum and 6 biopsies in colon will be taken. Additional blood samples (3x10mL heparin) will be taken prior to the ileocolonoscopy for simultaneous functional analysis (site specific: only sampling of heparin blood in Ghent University Hospital). A new MRI of the sacroiliac joints will be performed in all patients in which treatment was withdrawn because of sustained clinical remission on 2 consecutive clinical visits. For all those patients the study ends and follow-up and treatment will be foreseen every 6 months in our local Be-Giant register according to the routine clinical practice.

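### Section 8 leaves systemic corticosteroids and DMARDs for axSpA unrestricted in the NSAID phase, although ASDAS alone decides the golimumab switch and sustained remission (minor)

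*Combined protocol and SAP*

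**What the plan says.** The in-trial rule on other drugs is one sentence in section 8, which sets "no specific limitations for concomitant therapy, with exception of the use of DMARDs or other biologicals, while on therapy with golimumab". The rest of section 8 repeats entry criteria from 6.1.3, such as "Exposure to systemic corticosteroid treatment in the last 14 days before the ileocolonoscopy" and a 3-month DMARD-free period before the same procedure. Section 6.1.5 adds only contraception: "There are no specific limitations for the participants other than the ones listed at section 6.1.3 Exclusion criteria".

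Treatment starts with an NSAID: "All subjects will receive a full anti-inflammatory dose NSAID for 2 weeks according to the routine clinical practice". A patient stays on it if ASDAS is below 1.3, or has fallen by at least 1.1 to no more than 2.1. Otherwise a second NSAID follows for 2 weeks, judged by the same rule. Then: "If this disease activity state is not reached at week 4, the NSAID treatment will be stopped and subjects will start treatment with golimumab". Section 6.2.2 gives golimumab as monotherapy.

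Under 6.2.4, with ASDAS below 1.3 at two consecutive visits 12 weeks apart, "subjects are considered to be in sustained clinical remission and golimumab or NSAID therapy will be stopped". The primary endpoint in 3.4 is the same state: "Clinical remission, evaluated on 2 consecutive follow-up visits". Primary objective 2 in 3.1 begins "To evaluate whether there is a higher need of anti-tumor necrosis factor" and compares patients with and without gut inflammation.

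**The concern.** The protocol treats steroids and DMARDs as able to disturb its measurements. It excludes recent use before the baseline ileocolonoscopy, bars DMARDs and other biologicals during golimumab, and gives golimumab alone. The NSAID phase, which decides who goes on to golimumab, has no such restriction.

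There are two separate consequences.

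- **Switch.** The only written switch rule is at week 4. The plausible case is a short steroid course before then that brings ASDAS under the threshold, so that the patient stays on the NSAID. This touches objective 2 if need is counted as starting golimumab; the protocol does not define it.
- **Remission.** A steroid or DMARD added later, in a patient kept on an NSAID, cannot affect the week-4 decision. It could still lower ASDAS below 1.3 at two visits and yield a counted sustained remission.

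The golimumab phase is not at issue, because 6.2.2 specifies monotherapy.

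**Working it through.** **Step 1: what is restricted, and when.**

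| Drug | Before entry (6.1.3) | NSAID phase | On golimumab |
|---|---|---|---|
| Systemic corticosteroid | None in the 14 days before ileocolonoscopy | No limit | Not named in section 8; monotherapy in 6.2.2 |
| DMARD | None in the 3 months before ileocolonoscopy | No limit, on the natural reading | Barred |
| Other biological | No prior exposure to one that could affect SpA | No limit, on the natural reading | Barred |

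The last clause of the section 8 sentence limits its exception to golimumab treatment. If the comma is read so that DMARDs and biologicals are barred throughout, systemic corticosteroids are still unrestricted in the NSAID phase.

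**Step 2: plan figures.** No figure in the plan bears on this point. Section 10.1 sizes the trial (55 per group, 110 on golimumab, 80% power) for ASDAS below 2.1 after golimumab and does not print the pilot proportions. What follows uses assumed inputs.

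**Step 3: effect on the switch.** Let p1 and p2 be the proportions who would switch with and without gut inflammation, and r the fraction of would-be switchers kept off golimumab by an added drug, equal in both groups. The observed difference is

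p1(1 - r) - p2(1 - r) = (1 - r)(p1 - p2).

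The shrinkage does not depend on p1 and p2: x0.98, x0.95 and x0.90 for r = 2%, 5% and 10%. If 110 of the 147 patients would switch (an assumption: 10.1 gives 110 and 6.1.1 gives 147, but nothing links them), that is 110r = 2.2, 5.5 and 11.0 patients, all within 4 weeks of baseline.

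**Step 4: hypothetical power.** Two proportions, pooled variance, two-sided 5%, 74 and 73 patients, assumed switch rates averaging about 75%:

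| Assumed rates | r = 0 | 2% | 5% | 10% |
|---|---|---|---|---|
| 80% v 70% | 29% | 27% | 25% | 21% |
| 85% v 65% | 81% | 77% | 73% | 65% |
| 90% v 60% | 99.2% | 98.6% | 97.5% | 94.6% |

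At r = 2% the loss is about 0.6 to 3 points. The trial was not sized for this comparison, so the table only shows sensitivity.

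**Step 5: effect on remission.** Each co-medicated patient counted in sustained remission adds 1/147 = 0.7 points to the overall rate; four would add 4/147 = 2.7 points. Where such patients fall in both gut groups, the effect on the difference between groups is smaller.

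**The case against.** The strongest reply is that 6.2.2 already prescribes a closed sequence: responders stay on what they have, and non-responders take a second NSAID and then golimumab. Section 6.5 lists only NSAIDs and golimumab. An added steroid is off that path, and the incentive runs against it, since golimumab is supplied (4.3) and 6.1.6 presents access to it as an advantage. An r of 10% would need at least 11 of 110 would-be switchers to be treated this way and to respond; nothing in the documents suggests that. This stands, and it keeps the point small. It does not close the gap, because section 8 expressly permits what the sequence merely omits. The flowchart in 6.3 is not visible in the text available, so it could not be checked.

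Section 7 blinds investigator and patient to the ileocolonoscopy until the switch, except for major abnormalities needing intervention. That makes use by gut status unlikely, but it does not prevent dilution.

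Section 6.2.7.3 records dosage and duration of medication at follow-up visits, so use could be found afterwards. It lists no indication, however, and 10.3 says only who will do the analysis. The handling would then be chosen with the data in view.

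It is also fair to say that the primary endpoint is not attributed to any drug, and that objective 2 is affected only under one reading of need. Both limits are kept below.

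**Conclusion.** The gap is real and minor. In the NSAID phase a systemic corticosteroid, and on the natural reading a DMARD, may be given for axSpA while ASDAS alone decides the switch and sustained remission. The expected effect is a small dilution: a factor (1 - r) on the switch difference and about 0.7 points of overall remission per affected patient. This assumes equal use in the two gut groups and, for the switch, that need means starting golimumab. Frequency is unknown and probably low.

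Three stronger readings are not supported.

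- **Bias by gut status.** A reader might infer that the comparison is biased in a particular direction. Blinding lasts until the switch, so it covers the NSAID phase apart from the major-abnormality exception.
- **A large rise in remission on NSAID.** With 147 - 110 = 37 patients left on NSAID, one to four affected patients would be 1/37 to 4/37, or 2.7 to 10.8 points. The protocol sets no NSAID-specific remission rate as an endpoint, and the 37 rests on the unstated link between 110 and 147.
- **A material loss of power.** The figures in the table rest on assumed rates for a comparison the trial was not sized for.

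**What to change.** Extend section 8: no systemic corticosteroid, DMARD or non-study biological is given for axSpA during the NSAID phase. A patient judged to need one is an NSAID failure, is not counted in sustained remission on NSAID, and moves to golimumab under the 6.2.2 rule.

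For breaches, report objective 2 in two ways: as started anti-TNF, and with these patients counted as needing anti-TNF. The first count alone would still class a patient kept off golimumab by a steroid as not needing it.

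Record the indication next to the medication data already collected under 6.2.7.3. Flag systemic steroid use for other indications without counting it as failure, and add a sensitivity analysis that excludes ASDAS assessments made under it.

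The cost is one clause, a short analysis rule and one CRF field, with no added visit, procedure or patient. Clinicians lose a little freedom in the NSAID phase, and a few patients who might have stayed on the NSAID will be counted as failures.
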